Exclusion Criteria:	
 
• Previous surgical or cosmetic procedure to the target area in the last 6 to 12 months that could interfere with the treatment procedure
 
• A study participant must not be pregnant or have been pregnant in the last 3 months
 
• A recent history of smoking (6 months)
 
• Presence of an active skin disease or condition that may affect wound healing (ie. diabetes myelitis; connective tissue disease; radiation therapy; or chemotherapy)
 
• Seizure disorder caused by bright light
 
• A history of thrombophlebitis
 
• A history of acute infections
 
• A history of heart failure
 

	
 
• Cancer, malignant disease, skin pathology, condition, or allergic reactions that could interfere with evaluation or with the use of typical ancillary medical treatments or care used before, during, or after treatments
 
• Received or is anticipated to receive antiplatelets, anticoagulants, thrombolytics, vitamin E, or anti-inflammatories within 2 weeks prior to treatment
 
• Intolerance or allergy to medications that could be prescribed before or after the procedure (eg, antibiotics, anesthesia)
 
• A history of keloids
 
• A history or evidence of poor wound healing
 
• A history of coagulative disorder or current use of anticoagulant drugs within 2 weeks of study participation
 
• Use of steroids within 2 weeks of study treatments
 
• Patients with implanted pacemaker or defibrillator, or metal pins, or prosthetic joints within 4 cm of treatment area
 
• History of psychoneurosis and/or a history of alcohol or drug abuse
 

Primary Endpoint:	
 
• Group A: Evaluation of randomized before treatment and 3-month follow-up images by blinded evaluators
 
• Group B: Complete wound healing following the treatment assessed by collected biopsies.
 

Secondary Endpoints:	
 
• Adverse Event Assessment
 
• Subject satisfaction
 
• Physician satisfaction
 
• Subject Clinical Global Aesthetic Improvement Scale
 
• Physician Clinical Global Aesthetic Improvement Scale
 
• Histological Evaluation
 

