## 2.3 POTENTIAL RISKS AND BENEFITS

### 2.3.1 KNOWN POTENTIAL RISKS

This treatment modality was designed to inherently minimize the risk to the participant. As with any laser device treatment, there is a risk of adverse events, skin reactions or side effects. Expected side effects include:

- Discomfort: When a pulse is triggered, it may cause various degrees of discomfort. Some describe the sensation as stinging. A burning sensation may last for up to an hour after treatment.
- Blistering and burns
- Discoloration: Every laser treatment carries the possibility of permanent skin discoloration. Post-inflammatory hyperpigmentation and pigmentation are widely known complications of laser treatment.
- Eye injury: Protective glasses or goggles are provided for operators and assistants. It is extremely important to wear eye protection at all times during treatment to protect the eyes from accidental exposure to laser and serious injury.
- Infection: Every scar left on the skin carries the risk of infection. This risk of infection may also be associated with machines such as the MOSAIC ULTRA laser system. If detected, any infection should properly be treated with topical and/or systemic medications.
- Keloid formation: Scars may become thickened due to excessive growth of fibrous tissue.
- Prolonged redness: A mild case of temporary red spots is an expected reaction. However, if the red spots appear severe or last much longer than expected, do not repeat the treatment until the spots have disappeared. This reaction may vary by patient.

- Scarring: There is a possibility that scars may form due to treatment with the MOSAIC ULTRA laser system. Scars may form locally if treatment procedures are not properly followed, which may lead to exposure to laser, infection or physical irritation of the area such as wiping or rubbing.
- Delayed wound healing/skin textural changes: After laser treatment, the reepithelialization process may not proceed as expected due to the patient's physiological characteristics (e.g. lack of wound healing ability or poor care after treatment). This may result in undesirable changes to the skin texture.
- Temporary bruising

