### 3. OBJECTIVES AND PURPOSE

The objective of this study is evaluate the safety and effectiveness of the Mosaic Ultra laser system for the treatment of cutaneous lesions, periorbital wrinkles, acne scars, and surgical scars.

For subjects in group B, the primary objective will be evaluation of the histological changes via post-treatment biopsies to confirm appropriate wound healing post treatment

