#### 4.4 SUCCESS CRITERIA

The study will be considered a success if the following criteria are met:

Group A: Clinical Treatment Arm

1. Blinded evaluators are able to correctly identify the post-treatment image at least 80% of the time
2. The adverse event and side effect profile are acceptable

Group B: Biopsy Arm

1. Wounds induced by the treatment device appropriately healed as assessed by histology.

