#### **6.4 FOLLOW-UP VISITS**

Post-treatment follow-ups may occur up to 7 days post-treatment. These follow-ups are optional and may be conducted in-phone, over email, or in-person as determined by the clinician. If an optional post-treatment follow-up is determined necessary by the clinician the subject will be notified before the end of their treatment visit and the visit will be scheduled at that time. Adverse events will be evaluated at this visit. If subject has elected to participate in the biopsy portion of the study then a biopsy may also be collected at this visit.

In-person follow up visits will occur  $30\pm 7$  and  $90\pm 14$  days post final treatment. Adverse events will be assessed at these visits. Subjects will be asked to rate their satisfaction (Table 3) with their overall results as well as grade their improvement on the CGAIS (Table 4).

Subjects in Group B will then return 3 and 14 days post treatment to have an additional biopsy collected from the treated area. Subject's will then return for a final follow-up for biopsy collection between 19 and 90 days post treatment. Photos will be taken at all visits to ensure proper collection of biopsies as well as to capture the skin response.

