## 7.3 TIME PERIOD AND FREQUENCY FOR EVENT ASSESSMENT AND FOLLOW-UP

The occurrence of an AE or SAE may come to the attention of study personnel during a study visit or upon review by a study monitor. All ETEs and AEs will be captured on the appropriate data form. Information to be collected includes event description, date of onset, clinician's assessment of seriousness and severity, relationship to study device/treatment (assessed only by those with the training and authority to make a determination), actions taken, and date of event resolution. All AEs occurring while on study must be documented appropriately regardless of relationship. All ETEs/AEs assessed as "not yet resolved" must continue to be followed via telephone contact, by email, or clinic visit every 7 days or sooner (as per the physician's direction until event resolution or stabilization or tissue resection).

A pre-existing condition should not be reported as an adverse event unless there has been a substantial increase in severity or frequency of the problem that has not been attributed to natural history.

Changes in the severity of an event will be documented to allow for a determination if the event should be re-categorized from an ETE to AE.

The PI will record all reportable events, with start dates, occurring any time after informed consent is obtained until seven days (for non-serious AEs) or 30 days (for SAEs) after the last day of study participation. At each study visit, the investigator will inquire about the occurrence of ETEs/AEs/SAEs since the last visit. Events will be followed for

outcome information until resolution or stabilization.

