## 9. STATISTICAL ANALYSIS

### 9.1 STATISTICAL AND ANALYTICAL PLANS

The primary analysis of efficacy will be by study group and will be based on the evaluable treated participants; hence, only those participants who received complete study treatments and completed a 30-day/90-day follow-up visit post-the-final-treatment-visit, and who have evaluable post-treatment images, will be included in the analysis. Analyses of safety will include all participants who received (complete or incomplete) study treatment.

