### 9.2 ANALYSIS DATASETS

The following analysis sets will be defined for the statistical analysis of this investigation:

Safety Evaluation Set (SES)

Subset of all participants who received the investigational treatment.

Full Analysis Set (FAS)

Subset of participants in SES that received complete treatments have primary effectiveness data available.

Per Protocol Set (PPS)

Subset of all participants who received complete treatments and have completed the study without major protocol deviations.

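### Group B's healing standard is worded in conflicting ways with no deciding biopsy named, and section 9.1's evaluable rule does not fit a histology arm

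*Combined protocol and SAP*

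**What the plan says.** All references are to the combined protocol and SAP.

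- **Standard.** The synopsis gives Group B's primary endpoint as "Complete wound healing following the treatment assessed by collected biopsies". Section 3 gives the objective as "evaluation of the histological changes via post-treatment biopsies to confirm appropriate wound healing post treatment". Section 4.3.1 speaks only of observing treatment effect and healing in punch-biopsy samples. Section 4.4 makes success depend on this: "Wounds induced by the treatment device appropriately healed as assessed by histology".
- **Biopsies.** Five are planned per participant: a control, one immediately after treatment, and one each at Visits 4, 5 and 6. For Visit 6, section 6.4 says "Subject's will then return for a final follow-up for biopsy collection between 19 and 90 days post treatment". Table 5 gives the same range and no target day.
- **Who is analysed.** Section 9.1 runs the primary efficacy analysis by study group. Besides complete treatment, it requires that participants "completed a 30-day/90-day follow-up visit post-the-final-treatment-visit, and who have evaluable post-treatment images". Section 9.2 defines the Full Analysis Set (FAS) as "Subset of participants in SES that received complete treatments have primary effectiveness data available".
- **Healing risk.** Section 2.3.1 lists "Delayed wound healing/skin textural changes: After laser treatment, the reepithelialization process may not proceed as expected" among the known risks.

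**The concern.** Group B is the arm that judges healing by histology, and its result is one of the study's success criteria. Three things need to be settled before slides are read: what counts as healed, which biopsy shows it, and who is in the denominator. The first is worded in two ways, the second is not stated, and the third is written around visits and photographs that belong to Group A.

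A slide with partial re-epithelialisation could fail the synopsis endpoint and still pass section 4.4. Followed to the letter, section 9.1 would choose Group B participants by visit date and image quality instead of by whether a readable biopsy exists. The reported healing result could then change with choices made after the slides are known.

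**Working it through.** The documents give no sample-size, power or healing-time figure for Group B, so there is no stated result to reproduce. The check compares the texts and counts days.

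**1. The standard.** *Complete* appears only in the synopsis. *Appropriate* or *appropriately* appears in sections 3 and 4.4. Section 4.3.1 sets no standard. No section defines either word histologically, so *appropriate* could be looser or stricter than *complete*.

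**2. The deciding biopsy.** None of the synopsis, sections 3, 4.3.1, 4.4, 6.4 or 9 names one, or says how the serial biopsies would be combined into one verdict. Visit 6 is the natural candidate because it is last.
- Visit 6 window: 90 − 19 + 1 = 72 days.
- Elsewhere the schedule is tighter: ±1 and ±2 days for Visits 4 and 5, and ±7 and ±14 days for Group A's follow-ups.

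**3. The section 9.1 rule applied to Group B.** Group B has one scheduled visit after Day 14, namely Visit 6. Section 9.1 gives no windows of its own, so I assume those that section 6.4 attaches to the 30- and 90-day visits.
- 30 ± 7 is Day 23 to 37: 37 − 23 + 1 = 15 days, all inside the Visit 6 window.
- 90 ± 14 is Day 76 to 104. The part inside the Visit 6 window is Day 76 to 90: 90 − 76 + 1 = 15 days.
- If either visit is enough: 15 + 15 = 30 of the 72 permitted days qualify and 72 − 30 = 42 do not. Day 50 is among the 42.
- If both visits are needed: the two windows do not overlap, so one visit cannot meet both and no participant on the Group B schedule qualifies.
- Images: Table 5 schedules photographs at Group B's biopsy visits, so the image condition can be met in form. A Day 30 attendee with photographs and an unreadable biopsy would be admitted.

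**4. The FAS.** It asks for primary effectiveness data, which fits histology better. But section 9.1 does not refer to it, and it does not say which biopsy counts. A participant with only the Day 4 biopsy could enter.

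**5. Booking day, if Visit 6 alone decides.** Suppose a wound heals on Day D, stays healed and is read without error. It reads as healed when the biopsy day is at or after D. If D is 19 or earlier it always reads healed; if D is after 90 it never does. For D from 20 to 90 (90 − 20 + 1 = 71 days) the answer depends on the booking. This counts calendar days and is not an effect size.

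As an illustration only, assume lognormal healing times with median m and log-scale SD 0.4. The expected number healed of 30 at day t is 30 × Φ[(ln t − ln m)/0.4].

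| Assumed median m (days) | All biopsied Day 19 | All biopsied Day 90 |
|---|---|---|
| 10 | 28.4 | 30.0 |
| 14 | 23.3 | 30.0 |
| 21 | 12.0 | 30.0 |
| 30 | 3.8 | 29.9 |

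The effect runs from negligible to dominant depending on a median that the documents do not give.

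**The case against.** The strongest reply is that this is a descriptive pilot. No section defines a healed count or proportion, and section 4.3.1 reads as serial observation. Read as a course, Visits 4 and 5 already help to separate early from late healing, and the booking of Visit 6 matters less. This stands in part: booking dependence is conditional on the last biopsy deciding. It does not remove the gap, because no rule for scoring the course is given either.

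On section 9.1, a reader might infer that Group B would have no evaluable participants. The documents do not support that as a prediction. The slash between the two visits is ambiguous, the FAS offers another route, and the 30/42 split borrows windows written for Group A. Healing could also be handled as safety, where section 9.1 includes everyone treated. But the synopsis and section 4.3.1 make histology Group B's primary endpoint, and no section sends it to the safety analysis. The misfit in the wording remains.

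A reader might also infer that slow healing would go unseen. The documents do not show this. People with poor wound healing are excluded by section 5.3, and section 7.3 says unresolved events "must continue to be followed via telephone contact, by email, or clinic visit every 7 days or sooner".

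Finally, a reader might conclude that Visit 6 should be cut to Day 30 ± 7. That is a trade-off, not a correction. The synopsis ties Group B's treatment parameters to regulatory requirements and the revisions log ties its size to data required by FDA, but the request itself is not in the documents, so the reason for the wide window is unknown. Narrowing would lose all histology from Day 38 to 90. It could also shorten follow-up: section 7.3 follows events to resolution or stabilisation, while section 7.4.1 stops adverse-event follow-up at the final study visit, which for Group B is Visit 6.

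**Conclusion.** The point holds for the standard, the deciding biopsy and the evaluable set. The conflict in wording and the misfit of section 9.1 rest on the text alone and hold whatever the healing times are. Taken literally, section 9.1 can exclude schedule-compliant participants with readable biopsies and include one without.

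The dependence on booking is real only if Visit 6 alone decides, and only for wounds not healed by Day 19. The 72-day window is a fact of the schedule; how many of up to 30 participants it would affect cannot be estimated. The table above rests on assumed healing times and should not be cited as an estimate.

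A related gap is that section 4.4 does not say how many participants must heal or who reads the slides. The documents give no basis for proposing a number.

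**What to change.** 1. Use one standard in the synopsis and in sections 3, 4.3.1 and 4.4: complete histological healing, defined before any slide is read. One example is continuous re-epithelialisation over the treated zone with no residual coagulated tissue, for the pathologist to confirm.
2. Name Visit 6 as the deciding biopsy.
3. In section 9.1, define Group B's evaluable set as treated participants with a readable Visit 6 biopsy, and report missing or unreadable ones separately.
4. Report the number healed at Visits 4, 5 and 6 with actual biopsy days and exact 95% intervals. With 30 readable biopsies, 30 healed gives 88.4% to 100%, and 27 healed gives 73.5% to 97.9%. Actual days also cover the difference between Table 5 (Day 4 ± 1 and 12 ± 2) and section 6.4 (3 and 14 days) for the early biopsies.
5. Keep Day 19 to 90 unless the regulator's request allows a target day. Narrow it only after sections 7.3 and 7.4.1 are reconciled so that an unhealed wound is followed beyond the final visit.

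The cost is wording, minor extra reporting and possibly a less favourable healed figure. No biopsies are added. Because Visit 6 would decide while its window stays open, some dependence on booking remains; reporting the actual days makes it visible.

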### 5. PARTICIPANT ENROLLMENT AND WITHDRAWAL

#### 5.1 PARTICIPANT ENROLLMENT

The study population will consist of male and female patients between 20 and 60 years old who have chosen to participate in this clinical trial as evidenced by execution of the informed consent document.

##### 5.1.1 INFORMED CONSENT

Investigators have ethical and legal responsibilities to ensure that the protocol is clearly explained to each participant considered for enrollment in the study. Compliance with this requirement should be documented on a written Informed Consent Form approved by the reviewing IRB. Each Informed Consent Form will include the elements required by FDA regulations in 21 CFR Part 50.

The IRB-approved Informed Consent Form will be signed by the study personnel obtaining consent. The participant will be given a copy of the signed Informed Consent Form. The investigative site will keep the original on file.

Written informed consent will be obtained from all participants (and/or parents, guardians, legal representatives) before any study-related procedures, including any pre-treatment screening procedures, are performed. Investigators, or delegated study personnel, may discuss the availability of the study and the possibility for entry with a potential participant without first obtaining consent. Informed consent must be obtained and documented prior to initiation of any procedures that are performed solely for the purpose of determining eligibility for research.

##### 5.1.2 PRE-TREATMENT RECRUITING/SCREENING

Participants will be recruited from the study site's patient database or IRB-approved advertisement and then subsequently screened. Study site personnel will explain the design and purpose of the study to potential study participants. Participants interested in participating will visit the study site where informed consent will be obtained.

###### 5.1.2.1 SCREEN FAILURES

A screening failure participant is one from whom informed consent is obtained and is documented in writing (ie, participant signs an Informed Consent Form), but who does not receive a test spot exposure visit because of failure to meet all of the eligibility criteria. Screening failure participants will be included in the total number of participants enrolled (ie, all participants consented), but not counted towards the total participants treated.

#### 5.2 PARTICIPANT INCLUSION CRITERIA

Participants must meet all of the following criteria for study enrollment:

- Non-smoking, Male or Female
- Age 20 – 60 years old
- Understands and accepts the obligation not to undergo any other procedures in the areas to be treated.
- Participants who are willing and able to comply with all study participation requirements including returning for follow-up visits and abstaining from exclusionary procedures for the duration of the study.
- Participants who are willing to undergo biopsies.

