Hair loss and hair thinning is a common issue where the hair stops naturally growing in certain spots and is typically only a concern when this occurs on the head. There are a variety of reasons this can occur but the general idea to treat this issue is by promoting cell proliferation, increasing overall cell survival and promoting the anagen phase of the hair follicles.

There are a variety of treatment options such as topical therapies (tretinoin or topical vitamin C), cryotherapy, and various lasers and energy delivery devices that have been developed to improve skin tone and texture, facial rejuvenation, photoaging, wrinkles, scars, stretch marks, acne vulgaris and hair loss.

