#### 2.3.1.2 SAFETY VARIABLES

Prior to the first exposure, the participant's medical history will be reviewed, pregnancy history will be documented, and a physical examination of the treatment area will be conducted to ensure it is free of open wounds. At each subsequent visit, the participant will be queried about adverse events and changes in concomitant medications, and the exposure area will be visually examined.

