#### PRIOR TO TAKING PHOTOGRAPHS:

- Natural Skin; skin washed, and no make-up
- Jewelry removed
- For any body part being treated, ensure a black background is in place
- Treatment area may be marked with a surgical marker prior to photographs

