#### AFTER TAKING PHOTOGRAPHS (*before participant leaves the office*):

- Ensure all views have been taken
- Ensure all photographs are in focus
- Ensure lighting is consistent
- Ensure all follow-up photographs are similar to baseline images in views, angles, lighting, placement, and distance.

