### 6.3.5 POST-TREATMENT CARE

Participants will be advised:

- Do not use any scrubbing product for one week after treatment.
- Do not use functional cosmetics (eg, retinol, AHA) for 2 days.
- Avoid saunas for at least one week.
- Do not use cosmetic products (toner, lotion) containing alcohol. They may cause skin irritation. Use a mild moisturizer.
- Apply sun block cream (SPF 30, PA++) everyday, to prevent PIH. It is advisable to wear a hat and take an umbrella when going outside for 30 days after the procedure.
- Skin Dryness are normal reactions associated with the thermal effect, so please apply moisturizing cream frequently.

For subjects in Group B, post-biopsy instruction will be provided to the participant. The participant will be instructed to not fully submerge the biopsy site in water. The bandage or coverings for the biopsy site should be changed on a daily basis and should also be changed if it becomes wet or damp. The subject will also be told that once a scab or new skin begins to grow over the area and that the bleeding from the biopsy site has stopped they can discontinue the wound treatment regimen and remove the bandage.

Other post-treatment procedures will be considered and used as deemed by a clinician to be standard and reasonable care. Participants will be instructed that blistering, bleeding, oozing, strong pain, excessive swelling persisting for more than 48 hours, or signs of infection (eg, itching; pus; drainage; fever; chills) are cause for immediate concern.

There is a risk of an allergic reaction to the anesthetic or oral medication used in treatment and/or the biopsy. An allergic reaction to the anesthetic may cause: hives, itching, swelling, faintness, low blood pressure, difficulty breathing, and life-threatening shock. In the event of the aforementioned infection or allergic reaction scenarios, immediate emergencies (medically unstable) must be triaged in emergency care.

If the aforementioned side-effects are not an immediate emergency (medically stable), participants should contact the investigator and/or his designee, to be evaluated and potentially treated at no cost to the participant. An unscheduled visit will be arranged so that the Investigator can clinically evaluate and photograph these findings.

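### Topical and drug treatment of the treated condition is not held stable between the baseline and 90-day photographs in Group A, and no analysis uses the changes that are recorded.

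*Combined protocol and SAP*

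**What the plan says.** **Success rule.** Group A is non-randomized and every participant is treated. Section 4.4 sets its efficacy criterion: "Blinded evaluators are able to correctly identify the post-treatment image at least 80% of the time". The synopsis specifies 3-month images.

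**Other treatment.** Section 5.2 requires that each participant "Understands and accepts the obligation not to undergo any other procedures in the areas to be treated", and also commits them to "abstaining from exclusionary procedures for the duration of the study". Both clauses concern procedures. Section 6.3.5 adds "Do not use functional cosmetics (eg, retinol, AHA) for 2 days". Section 2.1.2 lists tretinoin and topical vitamin C among the existing options for the study indications: "There are a variety of treatment options such as topical therapies (tretinoin or topical vitamin C".

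**Photographs.** Section 6.1 requires "Natural Skin; skin washed, and no make-up" on the day and "Ensure all follow-up photographs are similar to baseline images in views, angles, lighting, placement, and distance".

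**Recording and analysis.** Under section 2.3.1.2, at each later visit "the participant will be queried about adverse events and changes in concomitant medications". Section 6.5 sends prescription, over-the-counter and non-prescription medications to the CRF. Section 9.1 selects participants by complete treatment, follow-up and evaluable images. Section 9.2 removes major deviations from the Per Protocol Set. Section 9.3 is descriptive. None of the three mentions concomitant treatment.

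**The concern.** The Group A result is a before/after comparison with nothing beside it. Whatever else alters the skin between the two photographs enters the same percentage as the device.

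Take a photoaging participant who starts tretinoin 30 days after the last session. If the 90-day image looks better for that reason, the evaluators pick it and section 4.4 counts a correct identification. A participant who gives up a long-used topical may look worse and count against the device. Neither has broken a visible rule, so neither has a protocol deviation, and both stay in the primary analysis and the Per Protocol Set. At stake is whether a percentage close to 80% can be read as the effect of the device.

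**Working it through.** **1. Does any existing rule hold the regimen stable to the 90-day photograph?**

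| Section | What it controls | Stable topical or drug regimen to day 90? |
|---|---|---|
| 5.2 | Other procedures, whole study | No; topicals and drugs are not procedures |
| 5.3 (exclusion criteria) | Steroids within 2 weeks of study treatments; anti-inflammatories and vitamin E within 2 weeks before treatment | No; tied to treatment dates; no retinoid, vitamin C or AHA named |
| 6.3.5 | Retinol/AHA 2 days; scrubs 1 week; alcohol-containing products, no end date | No; retinol/AHA may resume after 2 days |
| 6.1 | Make-up and photographic conditions | No |
| 2.3.1.2, 6.5 | Medication changes queried, medications recorded | Recorded, not restricted; cosmetic products unclear |
| 9.1 to 9.3 | Analysis sets and summaries | Records not used |

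**2. Length of the open period.** For retinol/AHA-type products only, the pause leaves 90 − 2 = 88 of the 90 days after the final session. On the Table 5 schedule it leaves at least 230 − 5 × 2 = 220 of 230 days. At the 6-week spacing that section 6.3 allows, the last photograph falls at 4 × 42 + 90 = 258 days, or 272 with the 14-day window.

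**3. Sensitivity of the 80% rule.** The plan gives no sample-size derivation, error rate or usage rate, so there is no figure to reproduce. The following are scenarios. Assume 180 evaluable participants, one judgement each, and changes unrelated to device response. The threshold is 0.80 × 180 = 144. Let p be the correct rate from the device alone, s the share who change treatment, and c the correct rate among them. Then

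q = p(1 − s) + c·s, and the pass chance is P(X ≥ 144) with X ~ Bin(180, q).

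| p | Change | c | q | P(X ≥ 144) |
|---|---|---|---|---|
| 0.75 | none | – | 0.750 | 0.069 |
| 0.75 | 10% start | 0.9 | 0.765 | 0.154 |
| 0.75 | 10% start | 1.0 | 0.775 | 0.240 |
| 0.75 | 20% start | 0.9 | 0.780 | 0.293 |
| 0.75 | 20% start | 1.0 | 0.800 | 0.544 |
| 0.85 | none | – | 0.850 | 0.973 |
| 0.85 | 10% stop | 0.5 | 0.815 | 0.735 |

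The stopper row assumes that stopping only cancels the visible device effect, leaving a coin flip (c = 0.5). A lower c would mean that treated participants look worse than at baseline, and nothing in the documents supports assuming that.

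**4. Inactive device.** With p = 0.50, the expected rate reaches 80% when s = (0.80 − 0.50)/(c − 0.50). That is 60% at c = 1.0 and 75% at c = 0.9.

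**5. What setting changers aside can and cannot show.**
- If 144/180 are correct and all 18 changers (10%) are among them, the rest score (144 − 18)/(180 − 18) = 126/162 = 77.8%, which is below the criterion.
- If changes are unrelated to device response, 162 remain and 130 correct are needed (0.80 × 162 = 129.6). The pass chance is 0.071 at p = 0.75 and 0.960 at p = 0.85, close to the no-change values.
- If the 18 starters are all device failures, a true 75% (135/180) reads 135/162 = 83.3% once they are removed. The pass chance is then 0.83 (18 failures removed from Bin(180, 0.75), needing X ≥ 130) or 0.88 (Bin(162, 135/162)). With everyone kept, and if the new treatment does not help, it is 0.069. Exclusion can therefore mislead.

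**The case against.** **Much is already controlled.** Procedures are barred for the study. Section 5.3 limits steroids, anti-inflammatories and vitamin E around treatment with no exception for topical forms, and sessions are 2 to 6 weeks apart, so those windows can cover much of the treatment phase. A reader might infer that participants may take any treatment, or that topicals in general are unrestricted. The documents support neither. What stands is narrower: no limit names retinoids, vitamin C or AHA beyond the 2-day pause, and none requires a stable regimen through follow-up.

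**The data are partly collected.** Prescription tretinoin would reach the CRF. That is correct, and it makes the remedy cheap. It does not cover cosmetic-grade products clearly, and no analysis is planned for what is recorded.

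**Unseen documents.** The operator manual and treatment guidelines are separate attachments, and the CRFs are not available here. A product restriction or CRF field could be there. The conclusion is limited to the protocol text.

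**It is a descriptive pilot.** A reader might infer that co-treatment favours the device, or could produce a pass for a device that does nothing. Starters and stoppers pull in opposite directions and no usage rate is given, so the direction is unknown. The 60% to 75% in step 4 makes the second inference implausible. Pilot status does not settle the matter, because section 4.4 sets a pass mark and section 2.2 says the study evaluates effectiveness.

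**Conclusion.** The point holds for topical and drug treatment of the treated condition, not for procedures. A permitted change of regimen can move the Group A percentage either way, and neither the design nor section 9 separates it from the device effect.

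Its size cannot be estimated from the documents. It matters for a result near 80%: in the scenarios above, 10% starters raise a 7% pass chance to between 15% and 24%, and 10% stoppers lower a 97% chance to 73%. These figures rest on 180 evaluable participants, one judgement each, changes independent of device response, and one assumed drug effect across indications as different as scars and hair loss. They show sensitivity and are not forecasts. The change is worth making because it is cheap and a regimen change not recorded at the time is hard to recover later.

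**What to change.** 1. **Sections 5.2 and 6.3.5.** From the baseline to the 90-day photograph, participants do not start, stop or change a topical retinoid, vitamin C or AHA product on the treated area, or a drug for the treated condition. Unchanged prior use, the 2-day pause, treatment of an adverse event, and the advised sun block and moisturiser stay allowed.
2. **CRF.** Record topical products used on the treated area at each visit, cosmetic products included.
3. **Section 9.1.** Keep the as-observed percent correct as the primary result that decides the 80% criterion. Beside it, report the numbers of starters and of stoppers, how many of each were correctly identified, and the percent correct without them. Label this supportive only, for the reason shown in step 5 of the working.

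The cost is one amendment, one CRF line and a small addition to one table. No control arm, participants or visits are added. The burden falls on participants, who keep a steady skin regimen for up to about 8 months on the Table 5 schedule (230 + 14 = 244 days), or about 9 months at 6-week spacing (258 + 14 = 272 days).
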